8. TREATMENT COMPLIANCE

The investigators and clinical trial coordinators will ensure appropriate patient treatment compliance according to the proposed treatment and surveillance timelines.

Patients will be informed that they have the right to withdraw from the study at any time for any reason, without prejudice to their medical care.

Patients who wish to stop taking the study medication will have the opportunity to remain in the study for long-term follow-up. The study will continue to monitor these patients for safety and oncologic treatment.

The Investigator will make every reasonable effort to keep each patient in the study unless it is in the patient's best interests to discontinue participation. If a patient is removed from the study or declines further participation, all End of Treatment evaluations should be performed if the patient is willing and able to be assessed. A description of the reason(s) for withdrawal from the study must be recorded on the case report form (CRF). The Investigator should also ensure that all patients are followed up for survival status after the Final Visit.

Patients who discontinue following entry will have relevant information completed and recorded on the CRF. All patients who discontinue because of adverse events or clinically significant laboratory abnormalities should be followed up until they recover or stabilize, and the subsequent outcome will be recorded. If any patient should die during the trial or within 30 days of stopping study treatment, the Investigator will inform the IRB. The cause of death should be recorded in detail, within 24 hours, on a serious adverse event (SAE) form and reported to institutional, federal and any other appropriate committees and/or sponsors.

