10. STATISTICAL CONSIDERATIONS

10.1 Study Design and Overview of Primary and Secondary Endpoints

This is a Phase II single-arm trial investigating the efficacy of the anti-PD-L1 antibody atezolizumab (Genentech) in the neoadjuvant setting for patients with regionally metastatic cutaneous head and neck squamous cell carcinoma with a historic or unknown primary. This will be an open-label trial reporting response rates with pCR as the primary endpoint.

Due to the nature of single arm and small sample size, we will not adjust our analyses for multiplicity, but we will present all outcomes we studied in the single paper with pre-specified designation of each outcome (e.g., primary or secondary/exploratory). Also, formal hypothesis testing will be avoided or properly accompanied/indicated by warning (e.g., a historical control for comparator or other comparability issues).

We will summarize continuous data at baseline with standard descriptive statistics, e.g., mean and SD (or median and IQR) and binary data with frequency and proportion. For continuous and binary outcomes data, point estimates and 95% CIs will be computed for appropriate parameter estimable (e.g., mean or median with accounting for censoring, if needed) and the Clopper and Pearson exact binomial method (with no censoring), respectively.

Primary Endpoints

Pathologic Complete Response (pCR)

pCR is defined as having no residual invasive squamous cell carcinoma within the primary tumor and all resected lymph nodes as assessed by the pathologist at the time of primary resection. The rate of pCR is defined as the proportion of patients demonstrating pCR.

Major Pathologic Response (mPR)

mPR is defined as having $\leq 10\%$ residual invasive squamous cell carcinoma within the primary tumor and all resected lymph nodes as assessed by the pathologist at the time of primary resection. The rate of mPR is defined as the proportion of patients demonstrating mPR.

Event Free Survival (EFS)

EFS is defined as the time from randomization to the first day of the any of the following events:

- Radiographic evidence of recurrence or disease progression per iRECIST
- Clinical evidence of recurrence or disease progression as assessed by clinical exam and confirmed by biopsy.
- Death due to any cause

A non-parametric Kaplan-Meier (KM) method will be used to estimate the 2-year EFS curve. Participants who do not experience recurrence or disease progression at the time of their last

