follow-up will be censored. Recurrence, all-cause death and disease-specific death will be likewise examined using the KM method to determine estimates of 2-yr disease-free survival, overall survival and disease-specific survival. Because we will use historical control (not concurrent control or parallel trial, despite the availability of raw data), we will try to focus on a description of results and 95% CI, instead of statistical significance.

Longitudinal data will be summarized similarly and accompanied by time points to illustrate possible trends. When we utilize historical controls (for description and informal comparison), we will use a control sample matched on key confounders (e.g., age, gender, key comorbidities and medical histories). We expect approximately 40 control patients, thus, achieving approximately 1:2 ratio in sample size for current sample: comparator.

Secondary Endpoints

FDG avidity of nodal disease sites as measured by PET

FDG avidity of nodal sites will be quantified according to standardized uptake value (SUV). The SUV is the ratio of the image derived radioactivity concentration of the lesion of interest and the whole body concentration of the injected radioactivity. SoC staging PET/CT will be performed prior to initiation of treatment and as a post-treatment scan 3 months after completion.

The association of the SUV of the regionally metastatic focus of disease to the pathologic response to neoadjuvant therapy at the time of surgery will be examined. A t-test (or nonparametric counterpart) and multiple regression will be used to compare mean SUV between patients who experience cPR to the mean SUV of those with residual disease after neoadjuvant therapy, where the latter will adjust patient characteristics and potential confounders. In addition, the mean SUV of additional sites of regionally metastatic disease will be studied.

Overall Response Rate by iRECIST

See Section 15.7.

Plasma exosome levels

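### As worded, the EFS censoring sentence in Section 10.1 censors deaths without recurrence or progression, although any-cause death is a listed EFS event

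*Combined protocol and SAP*

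**What the plan says.** Section 10.1 defines EFS as the time to the first of three events: radiographic recurrence or progression, biopsy-confirmed clinical recurrence or progression, and "Death due to any cause". Two-year EFS is to be estimated by Kaplan-Meier. The censoring rule follows in one sentence that runs over a page break: "Participants who do not experience recurrence or disease progression at the time of their last" and then "follow-up will be censored". The two halves join into a complete sentence, so no text appears to be lost between them. No other section gives an EFS censoring rule.

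The next sentence adds further curves: "Recurrence, all-cause death and disease-specific death will be likewise examined using the KM method to determine estimates of 2-yr disease-free survival", followed by overall and disease-specific survival. Section 10.1 also says that historical controls will be used "for description and informal comparison", and refers to them "despite the availability of raw data". The synopsis and the endpoint list in Section 2.2 name 2-year EFS as a secondary endpoint; they do not list DFS.

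**The concern.** The censoring sentence names two of the three kinds of event and omits the third. It does not require a censored participant to be alive. Someone who dies without recurrence or progression therefore has an event by definition and is censored by rule, and nothing in the documents says which prevails.

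If the sentence is programmed literally, each such death leaves the risk set without lowering the curve. The error can only go upward. It affects a listed secondary endpoint and any informal comparison with historical controls, which is fair only if both groups are handled by the same rules. Settling the wording before analysis also avoids a choice about deaths made with the results in view.

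**Working it through.** The documents give no expected EFS rate, event count or number of deaths, so there is no figure of the plan's own to reproduce. The size below is an illustration.

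**Inputs.** n = 18, from the synopsis and Section 10.2. Assumed: R participants with recurrence or progression and D deaths without either, all within the 2-year window, and no other censoring before 2 years.

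**Formulas.**
- Deaths counted as events: EFS = 1 − (R + D)/18.
- Deaths censored, all of them before the first recurrence (lowest value): EFS = 1 − R/(18 − D).
- Deaths censored, all of them after the last recurrence (highest value): EFS = 1 − R/18.

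Every other ordering lies between the last two values.

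**One case in full.** R = 4, D = 1. Counted: 13/18 = 72.2%. Censored: from 13/17 = 76.5% to 14/18 = 77.8%. The overstatement is 4.2 to 5.6 percentage points.

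| R | D | Death counted | Death censored | Overstatement (points) |
|---|---|---|---|---|
| any | 0 | 1 − R/18 | 1 − R/18 | 0 |
| 2 | 1 | 83.3% | 88.2–88.9% | 4.9–5.6 |
| 4 | 1 | 72.2% | 76.5–77.8% | 4.2–5.6 |
| 6 | 1 | 61.1% | 64.7–66.7% | 3.6–5.6 |
| 2 | 2 | 77.8% | 87.5–88.9% | 9.7–11.1 |
| 4 | 2 | 66.7% | 75.0–77.8% | 8.3–11.1 |
| 6 | 2 | 55.6% | 62.5–66.7% | 6.9–11.1 |

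The upper end is always D/18, which is 5.6 points per death.

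**Scale.** The Clopper-Pearson 95% interval for 13/18 runs from 46.5% to 90.3%, a width of 43.8 points. One misclassified death is small beside that.

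**How likely is such a death?** Inclusion criterion 11 in Section 4.1 requires a life expectancy of at least 2 years, so none or few is the likelier case. The secondary objective, however, places 2-year EFS after completion of adjuvant therapy. For patients with residual disease that comes after 15 cycles of 3 weeks, or 15 × 3 = 45 weeks, so on that reading the window runs past the period the criterion covers. Section 10.1 gives a different start for EFS. The illustration does not depend on which start is used, provided the assumed events fall inside the window.

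**The case against.** The strongest reply is that the definition governs. Section 10.1 states outright that death is an event. On an ordinary reading, censoring then applies to people with no event, and the sentence is merely incomplete. That is a fair account of the intent, and it rules out the stronger inference that the plan means to leave deaths out of EFS or has chosen a wrong endpoint. It does not remove the conflict, because this is the only censoring rule and nothing gives the event list precedence over it.

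A second reply is that all-cause death gets its own Kaplan-Meier curve and that all outcomes are to appear in one paper, so a discrepancy could be noticed. That helps detection but does not correct the EFS figure.

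A third is that the size rests wholly on assumed counts, is zero without such a death, and bears on a descriptive result. This stands, and it keeps the point minor.

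A reader might also infer that the plan mislabels a recurrence-only curve as DFS. List order suggests pairing recurrence with DFS, but that pairing is an inference. The sentence lacks the pairing word that Section 10.1 uses elsewhere, as in "the Clopper and Pearson exact binomial method (with no censoring), respectively", and it can be read as letting both recurrence and death feed DFS. What the text supports is narrower: it does not say whether death counts in DFS.

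**Conclusion.** The conflict is real and the correction is minor. Followed literally, the censoring sentence treats a death without recurrence or progression as censored and overstates 2-year EFS by roughly 4 to 6 points per such death at n = 18. This holds under the assumed 2 to 6 recurrences with no other censoring. If no such death occurs, nothing changes.

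No decision in the plan rests on EFS. It would go too far to infer any effect on the trial's main conclusion: pCR is assessed at surgery, and neither it nor the Simon stopping and success rules use the EFS censoring rule. The handling of death in DFS is a side note about an unlisted descriptive measure.

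**What to change.** Replace the censoring sentence in Section 10.1 with wording such as: *Participants alive and without recurrence or disease progression will be censored at their last disease assessment.* Naming the date matters because footnote 3 of the study calendar allows a video or phone visit, so last contact and last disease assessment can differ. Apply the same event and censoring rules to the historical controls as far as their data allow; the statement that raw data exist does not show that the data support identical rules. As a side note, state whether death counts in DFS, or label the curve as time to recurrence.

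The cost is two or three sentences, and the EFS figure may be slightly less favourable. New data collection is probably not needed, but the sources are not uniform. Section 8 says: "The Investigator should also ensure that all patients are followed up for survival status after the Final Visit". Section 9.5.2.6 asks for all later deaths whatever the cause. Against these, Section 9.4.1 limits reporting after the adverse event period to serious events attributed to study treatment, and Section 5.2.2 only permits the use of public records for survival status after withdrawal. The revised text should cite these sections together, so that deaths needed for EFS are collected on one stated basis.

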10.2 Sample Size Estimation / Evaluation of Efficacy / Accrual Rate

A Simon's two-stage design is used to calculate an optimal sample size and minimal efficacy threshold using a primary end-point of pCR. We assume an alpha type I error of 0.05 and power of 80% and set our response probability for an ineffective drug (p_0) at $pCR < 0.05$ and our response probability of an effective drug (p_1) at $pCR > 0.30$.

Sample Size

Given these parameters, a total of 18 subjects (n) with 3 or more responses would support continued investigation of the proposed treatment paradigm.

Evaluation of Efficacy

In stage 1 of our study, 5 (n_1) patient will be enrolled and if no responses are observed, the trial will be stopped early for futility.

Accrual Rate

We estimate an accrual of 1-2 patients per month, with a goal accrual of 18 patients in this trial

10.3 Evaluation of Safety

Safety and tolerability will be assessed through detailed history and physical at each clinical visit and documented using CTCAE v5. In addition, patients will complete EORTC QLQ-C30 and EORTC QLQ-H&N35 surveys at each clinic visit.

11. ADMINISTRATIVE REQUIREMENTS

11.1 Good Clinical Practice

The study will be conducted in accordance with the International Conference on Harmonisation (ICH) for Good Clinical Practice (GCP) and the appropriate regulatory requirement(s). The investigator will be thoroughly familiar with the appropriate use of the drug as described in the protocol and Investigator's Brochure. Essential clinical documents will be maintained to demonstrate the validity of the study and the integrity of the data collected. Master files should be established at the beginning of the study, maintained for the duration of the study and retained according to the appropriate regulations.

11.2 Ethical Considerations

The study will be conducted in accordance with ethical principles founded in the Declaration of Helsinki. The IRB will review all appropriate study documentation in order to safeguard the rights, safety and well-being of the patients. The protocol, Investigator's Brochure, informed consent, advertisements (if applicable), written information given to the patients, safety updates, annual progress reports, and any revisions to these documents will be provided to the IRB by the investigator.

11.3 Study Registration

Once signed, informed consent has been obtained and all pretreatment evaluations have been performed, patients will be entered on study according to UCD Office of Clinical Research (OCR) policy. To register a patient, the data manager or designee must complete the Eligibility Checklist and the Patient Registration Form. After verifying the eligibility, the OCR coordinator will register the patient onto the study and assign a patient accession. Administration of study drug may not be initiated until the patient is registered (See section 15.3, Registration Guidelines).

11.4 Patient Information and Informed Consent

After the study has been fully explained, written informed consent will be obtained from either the patient or his guardian or legal representative prior to study participation. The method of obtaining and documenting the informed consent and the contents of the consent will comply with ICH-GCP and all applicable regulatory requirement(s). In accordance with UCD OCR policy an original signed and dated participant Informed Consent document will reside in a secured location within the UCD OCR. Copies of the signed and dated Informed Consent document will be provided to the study participant and UCD Health System Information Management for inclusion in the participant's UCD Health System Medical Record.

11.5 Patient Confidentiality

In order to maintain patient privacy, all study reports and communications will identify the patient by initials and the assigned patient number. Data capture records and drug accountability records will be stored in secure cabinets in the UCD OCR. Medical records of patients will be maintained in strict confidence according to legal requirements. The investigator will grant monitor(s) and auditor(s) from Genentech or its designees and regulatory authority(ies) access to the patient's original medical records for verification of data gathered on the data capture records and to audit the data collection process. The patient's confidentiality will be maintained

and will not be made publicly available to the extent permitted by the applicable laws and regulations.

11.6 Protocol Compliance and Deviations

The investigator will conduct the study in compliance with the protocol given approval/favorable opinion by the IRB and the appropriate regulatory authority(ies).

All protocol deviations will be reported in accordance with UCD IRB Administration and UCD Cancer Center OCR policies. Any departures from the protocol must be fully documented in the source documents.

11.7 Premature Closure of the Study

This study may be prematurely terminated, if in the opinion of the investigator or Genentech, there is sufficient reasonable cause. Written notification documenting the reason for study termination will be provided to the investigator or Genentech by the terminating party.

Circumstances that may warrant termination include, but are not limited to:

1. Determination of unexpected, significant, or unacceptable risk to patients
2. Failure to enter patients at an acceptable rate
3. Insufficient adherence to protocol requirements
4. Insufficient complete and/or evaluable data
5. Plans to modify, suspend, or discontinue the development of the drug

11.8 Aggregate Reports

11.8.1 IND Annual Reports

Not applicable, as the study is IND exempt.

11.8.2 Other Reports

The Investigator will forward a copy of the Publication to Genentech within one year after last study visit.

11.9 Study Close-Out

Any study report submitted to the FDA by the Sponsor-Investigator should be copied to Genentech. This includes all IND annual reports and the Clinical Study Report (final study report). Additionally, any literature articles that are a result of the study should be sent to Genentech. Copies of such reports should be mailed to the assigned Clinical Operations contact for the study:

Atezolizumab IIS Clinical Operations: [contact]

And to Genentech Patient Safety CTV oversight mailbox at: [contact]

11.10 Record Retention

The investigator will maintain all study records according to ICH-GCP and applicable regulatory requirement(s).

11.11 Quality Assurance and Control

Quality assurance audits of select patients and source documents may be conducted by the UC Davis Comprehensive Cancer Center Quality Assurance Committee as outlined in the UC Davis Cancer Center Data and Safety Monitoring plan. Quality control will be maintained by the OCR Quality Assurance team according to OCR policy.

11.12 Data and Safety Monitoring

In addition to the requirements for adverse event reporting, this protocol is also subject to the UC Davis Comprehensive Cancer Center's (UCDCCC) Data and Safety Monitoring Plan. The UCDCCC is committed to pursuing high-quality patient-oriented clinical research and has established mechanisms to ensure both scientific rigor and patient safety in the conduct of clinical research studies. The UCDCCC relies on a multi-tiered committee system that reviews and monitors all cancer clinical trials and ensures the safety of its participants, in compliance with institutional and federal requirements on adverse event (AE) reporting, verification of data accuracy, and adherence to protocol eligibility requirements, treatment guidelines, and related matters. The Scientific Review Committee (SRC) assumes overall oversight of cancer studies, with assistance and input from two independent, but interacting, committees: the Quality Assurance Committee and the Data Safety Monitoring Committee. A multi-level review system strengthens the ability of the UCDCCC to fulfill its mission in conducting high quality clinical cancer research.

As per UCDCCC Office of Clinical Research (OCR) standard operating procedures, the principal investigator (PI) and clinical research coordinator (CRC) meet at least monthly for ongoing study information, to discuss patient data and adverse events, and to determine if dose escalation is warranted, when applicable.

According to the UCDCCC Data and Safety Monitoring Plan (DSMP), any new serious adverse events related to the drugs being used on this trial are reviewed at least every 3 months by the UCDCCC Data and Safety Monitoring Committee (DSMC) and any applicable changes to the study are recommended to the PI, if necessary. For study specific data safety monitoring: see section 12 for management, quality assurance, storage, and access to data; see section 9 for adverse event collection and reporting; and see section 11.7 for trial termination rules.

The UCDCCC Scientific Review Committee (SRC) determines if a UCDCCC Data and Safety Monitoring Board (DSMB) is required. If required, the DSMC will appoint a DSMB. The DSMB is responsible for reviewing study accrual logs, and adverse event information to ensure subject safety and compliance with protocol defined guidelines.

12. INVESTIGATOR REQUIREMENTS

12.1 Retention of Records

FDA regulations (21 CFR §312.62[c]) and the ICH Guideline for GCP (see Section 4.9 of the guideline) require that records and documents pertaining to the conduct of clinical trials and the distribution of investigational drug, patient records, consent forms, laboratory test results, and medication inventory records, must be retained for 2 years after the last marketing application approval in an ICH region or after at least 2 years have elapsed since formal discontinuation of clinical development of the investigational product. All state and local laws for retention of records also apply.

12.2 Study Medical Monitoring Requirements

This clinical research study will be monitored both internally by the PI and externally by the UC Davis Health IRB. In terms of internal review, the PI will continuously monitor and tabulate AEs. Appropriate reporting to the UC Davis Health IRB will be made. The PI of this study will also continuously monitor the conduct, data, and safety of this study to ensure that:

- Interim analyses occur as scheduled,
- Stopping rules for toxicity and/or response are met,
- Risk/benefit ratio is not altered to the detriment of the subjects,
- Appropriate internal monitoring of AEs and outcomes is done,
- Over-accrual does not occur,
- Under-accrual is addressed with appropriate amendments or actions, and
- Data are being appropriately collected in a reasonably timely manner.

Routine monitoring will be carried out via a periodic team conference among investigators during which toxicity data, including all SAEs, will be reviewed and other issues relevant to the study such as interim assessment of accrual, outcome, and compliance with study guidelines, will be discussed. Monitoring will be carried out on an ongoing basis. The severity, relatedness, and whether or not the event is expected will be reviewed.

